Project Title: A pilot study of stable kidney transplant recipients taking tacrolimus with CNS symptoms switched to Envarsus

Principal Investigator: [name]

Version Date: August 15, 2017

COMIRB #: 17-0781

Hypotheses and Specific Aims:

The use of once-daily Envarsus XR® (tacrolimus extended-release tablets) will have significant improvement in the patients reported CNS symptoms.

Background and Significance:

Graft survival in renal transplant patients has improved steadily over the last decades as a result of improved immunosuppressive therapies. Immunosuppressive regimens continue to have side effects which patients find burdensome and which may lead to sub-therapeutic dosing and non-compliance by the patient.

Patients on different immunosuppressant regimens may be bothered by Central Nervous System (CNS) side effects or report better health-related quality of life (HRQL). We will evaluate the reliability and validity CNS-specific outcome instruments (CNS Symptom Rating Scale; higher scores = increased severity) and Quality of Life Index (higher scores = better CNS-specific HRQL) in renal transplant patients.

Neurotoxicity in transplant patients occurs in >40-50% of the patients treated with tacrolimus (1). Tacrolimus was approved by the US Food and Drug Administration (FDA) in April of 1994 for the prophylaxis of organ rejection in patients receiving allogeneic liver transplants under the **brand name Prograf®** (tacrolimus capsules, Astellas Pharma US, Inc.).

The majority of the neurotoxicity events in tacrolimus treated transplant patients are headache and tremor, while less frequent and more severe neurotoxicity (encephalopathy, seizures) is also observed. (2) The current management of neurotoxicity varies by investigator and institution, but normally begins with a dose reduction of the tacrolimus, balancing increased risk of acute rejection and graft loss with the desire to improve the side effects observed for a given patient. (3, 4) In more severe cases, immunosuppressant regimens may be changed from tacrolimus to cyclosporine, an agent which also is associated with similar neurotoxicity and a reduced clinical effectiveness. Literature documents that the neurotoxicity is associated with peak tacrolimus concentrations in transplant as well as autoimmune diseases and shows that the neurotoxicity essentially abates when tacrolimus treatment is discontinued, providing proof that tacrolimus is a reversible neurotoxic agent. (5)

Envarsus XR (Veloxis Pharmaceuticals) is an extended-release formulation of tacrolimus designed for once-daily administration that has been developed utilizing Veloxis Pharma's proprietary MeltDose[®] drug-delivery technology (Veloxis Pharmaceuticals A/S, Hørsholm, DK). Envarsus XR is designed and has been approved by FDA to deliver equivalent whole blood concentrations to the immediate-release formulation of tacrolimus over the 24-hour dosing interval. As previously reported, The ASERTAA trial demonstrated that patients on Envarsus achieved therapeutic drug levels with a 30% lower peak concentration and 20% lower average dose compared to tacrolimus immediate-release regardless of genotype status. Importantly, patients expressing the CYP3A5*1 genotype on tacrolimus immediate-release reached a peak concentration as high as 26 ng/mL.

This high peak levels might related to the high incidence of CNS related side effects. The PK data collected for Envarsus XR[®] demonstrated similar exposure, lower C_{max}, prolonged T_{max}, and increased bioavailability when compared to tacrolimus immediate-release.

The study is designed in such a way that patient will report objectively their experience related to CNS symptoms using a standard questionnaire before starting on Envarsus XR. The OPTN/SRTR 2011 Annual Data Report shows that approximately 90% of Recipients transplanted in 2010 were initiated on tacrolimus as part of their immunosuppression regimen and were continuing to take tacrolimus at one-year post-transplant.

Envarsus XR is designed to deliver equivalent whole blood concentrations to the immediate-release formulation of tacrolimus over the 24-hour dosing interval. This formulation works better with the enzyme systems in the lower gastrointestinal (GI) tract, facilitating a constant stable absorption of tacrolimus through the GI tract leading to improved bioavailability and constant plasma levels over the full day.

In a prior study in stable renal transplant recipients converted from Prograf to Envarsus XR (LCP-Tacro), showed 30% greater bioavailability compared to Prograf, as well as a steadier and more consistent concentration time profile over 24 hours, and reduced peak-to-trough fluctuations and swing compared to Prograf, with good tolerability and a robust AUC/C_{min} correlation (correlation coefficients from 0.86 to 0.91).

A Phase III study in stable renal transplant recipients converted from Prograf to Envarsus XR demonstrated non-inferior efficacy and similar safety for Envarsus XR compared to Prograf. Total daily Envarsus XR dose was about 20% lower than preconversion Prograf twice-daily dose.

The Expanded access Study Envarsus 3007 conducted to provide patients the opportunity for an alternative tacrolimus treatment and/or continuation of therapy for patients previously on Envarsus clinical studies.

Envarsus XR tablets are an extended-release formulation of tacrolimus, intended for once-daily administration, the anticipated risks of Envarsus XR are expected to be the same as for Prograf though the severity and frequency may be less due to reduced maximal blood

concentrations. Based on the Prograf package, insert and the overall experience with Prograf in solid organ transplantation the anticipated risks from Envarsus XR include: nephrotoxicity, new onset diabetes mellitus, hypertension, neurotoxicity, hyperkalemia, and latent viral infections. Given the low peak tacrolimus levels when taking Envarsus, we might expect less CNS side effects. (6.7).

Overall, the study would provide renal transplant patients the opportunity to an alternative tacrolimus treatment with possible less CNS side effects.

CNS side effects are one of the main reasons that patients complain after having a kidney transplant while on tacrolimus (Prograf). The side effects can be debilitating and can affect patients overall well-being. In severe cases may lead to non-compliance. So the advantage of the study of using Envarsus XR for the patients is the ability to avoid those debilitating CNS side effects, like tremor, headache, and difficulty in concentrating and sleep disturbances. Envarsus XR has been approved and has similar efficacy as tacrolimus (Prograf, so there is no disadvantages or risk to the patients.

III. Preliminary Studies/Progress Report:

This is the first study on Envarsus XR using Patients reported questionnaire methodology to examine the CNS side-effects of Tacrolimus (Prograf). There is no need for a cross over study and each patient will serve as its own control. The design and methodology will be similar to the PROGIS study that was published by Chan et al (8).

Prior studies including the Phase III study in stable renal transplant recipients converted from Prograf to Envarsus XR demonstrated non-inferior efficacy and similar safety for Envarsus XR compared to Prograf. Total daily Envarsus XR dose was about 20% lower than preconversion Prograf twice-daily dose. Additional Expanded access Study Envarsus 3007 conducted to provide patients the opportunity for an alternative tacrolimus treatment and/or continuation of therapy for patients previously on Envarsus clinical studies. In addition to comparable efficacy and non-inferiority of Envarsus XR, there was better pharmacokinetics and possible less CNS side effects. However, the studies were not specifically designed to test this hypothesis.

IV. Research Methods

Outcome Measure(s):

This is a population-based, longitudinal, prospective, minimal risk interventional study of renal transplant patients in routine practice. This approach is designed to generate hypotheses (rather than test hypotheses) concerning the impact of current and newly emerging immunosuppressive regimens and decision-making on regimen tolerability, safety, patient co-morbidities, and graft and patient outcomes in the real world. We expect patients will have improvement in quality of life

related to sleep disturbance and upper extremity fine motor skills/ADL. Tacrolimus drug levels, serum creatinine and other parameters related to graft function, graft function, and other adverse events will be documented during the study period. Standard of care immunosuppression for kidney transplant recipients at UC Health is either Prograf twice a day or Envarsus XR once a day, Myfortic and steroids. Serum creatinine and tacrolimus levels (drug level monitoring) is required for both Prograf and Envarsus XR and is standard of care for this population.

Description of Population to be enrolled:

Inclusion

- Kidney transplant recipients with stable graft function will be switched from Prograf twice/day to Envarsus XR once a day per standard of care
- More than 1 months post-transplant
- 18+ years of age with some CNS problems secondary to Prograf (tacrolimus)

Exclusion

- Multi-organ patients (kidney/pancreas, kidney/liver)
- Evidence of graft rejection or treatment of acute rejection within 14 days prior to baseline visit
- Inability to self-administer the QOL questionnaires

Study Design and Research Method

Pilot study documenting the neurotoxic side effects including tremors in patients with stable graft who are receiving Tacrolimus following kidney transplantation. Standardized questionnaire will be used to document these symptoms. Envarsus XR® will be provided to the subjects by Veloxis Pharmaceuticals (manufacture of the drug) for the duration of the study (6 months). After a subject completes the study, they will continue taking Envarsus XR® through their insurance/self-pay.

Description, Risks and Justification of Procedures and Data Collection Tools:

After informed consent, the subject will complete the PROMIS questionnaire before switching to Envarsus XR. Subjects will repeat questionnaires at 1 month and 6 months focusing on quality of life (QOL) questionnaire related to sleep disturbance and upper extremity fine motor skill/activities of daily living (ADL)

Questionnaires

- Sleep Disturbance-Short Form 8a
- Upper Extremity Function (Fine Motor, ADL)-Short Form
- Upper Extremity-Short Form 7a
- Global Health Scale v1.2

Review medical record for demographics, medical history (including kidney transplant) and other basic information:

- vital signs,

- minimal lab collected as standard of care (serum creatinine, tacrolimus level)

Adverse events

Graft function

Potential Scientific Problems:

Each patient will serve as its own control. No scientific problem will be expected. Although the study is an open-label and no placebo group; but the patient reported outcomes will serve as its own control and any improvement in symptoms may not be placebo related as reported in previous studies using the same methodology.

Data Analysis Plan:

Research is conducted according to the ICH Harmonized Tripartite Guidelines for Good Clinical Practice and in compliance with the ethical principles of the Helsinki Declaration. Appropriate Institutional Review Board/Ethics Committee approval will be obtained prior to study initiation. Patients are eligible for participation if they are at least 18 years of age; willing to provide informed consent and adhere to study requirements; have received a renal transplant at least 1 month prior to the study enrollment; and have been on an immunosuppressive regimen including Tacrolimus (Prograf) for at least four weeks prior to enrollment.

All analyses will be performed with SAS version 8.02 (SAS Institute, Cary NC). Demographic variables and clinical conditions will be evaluated by descriptive analyses. For the descriptive analyses, chi-square tests will be used to evaluate categorical data; t-tests and analyses of variance (ANOVA) will be used to evaluate continuous data. Scoring – including imputations for missing data if necessary – will be performed according to each questionnaire's guidelines.

Reliability refers to the consistency of items within an instrument, either over time or internally within the instrument. Internal consistency reliability is the extent to which all items measure the same construct; values are presented descriptively, on an internal level scale from 0 to 1.0, with higher scores indicating a more reliable (precise) instrument

Summarize Knowledge to be Gained:

Immunosuppressive therapies have burdensome side effects which may lead to sub-therapeutic dosing and non-compliance.

The study will provide renal transplant patients the opportunity to an alternative tacrolimus treatment with possible less CNS side effects. CNS side effects are one of the main reasons that patients complain after having a kidney transplant while on tacrolimus (Prograf). The side effects can be debilitating and can affect patients overall well-being. In severe cases may lead to non-compliance. So the advantage of the study of using Envarsus for the patients is

the ability to avoid those debilitating CNS side effects and afford better compliance with the patients taking the medicine.

Study Calendar

Procedure	Baseline	M1	M6/EOS
Consent	X		
VS (BP, P, weight)	X	X	X
Serum creatinine	X	X	X
Tacrolimus level	X	X	X
Pregnancy test (as needed)	X		
Global health questionnaire	X	X	X
Sleep Disturbance-Short Form 8a	X	X	X
Upper Extremity Function (Fine Motor, ADL)-Short Form	X	X	X
Upper Extremity-Short Form 7a	X	X	X
Switch to Envarsus	X		
Adverse events		X	X

References:

1. Prograf[®] [package label]. Astellas Pharma US, Inc. Deerfield (IL); 2009

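### The aim promises significant improvement while the methods disclaim hypothesis testing; no form, visit or paired analysis is named, and the design cannot support the claim that improvement is not placebo related

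*Combined protocol and SAP*

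**What the plan says.** **Aim.** The single sentence under Hypotheses and Specific Aims says the switch "will have significant improvement in the patients reported CNS symptoms". It names no instrument, visit or size of change.

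**Purpose.** Research Methods, Outcome Measure(s), says: "This approach is designed to generate hypotheses (rather than test hypotheses". The end of Preliminary Studies/Progress Report leans the other way. It remarks that earlier studies were not set up to test this hypothesis, which implies that this one is.

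**Focus.** Outcome Measure(s) continues: "We expect patients will have improvement in quality of life" "related to sleep disturbance and upper extremity fine motor skills/ADL". The two domains are named together and neither is put first.

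**Schedule.** "Subjects will repeat questionnaires at 1 month and 6 months". The Study Calendar lists four forms at baseline, M1 and M6: Sleep Disturbance 8a, Upper Extremity Function (Fine Motor, ADL), Upper Extremity 7a and Global Health.

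**Analysis.** The Data Analysis Plan assigns t-tests, ANOVA and chi-square tests to descriptive analyses and leaves scoring to each questionnaire's guidelines. It gives no alpha, primary score, primary visit or analysis of change from baseline.

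**Instruments.** Background and Significance names a CNS Symptom Rating Scale and a Quality of Life Index. Neither is in the questionnaire list or the calendar.

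**Attribution.** Inclusion requires "18+ years of age with some CNS problems secondary to Prograf (tacrolimus". Potential Scientific Problems expects no scientific problem. It grants the limitation, "Although the study is an open-label and no placebo group", but then says "any improvement in symptoms may not be placebo related".

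**The concern.** The aim and the methods describe different kinds of study. A reader of the final report would not know whether a reported improvement was the planned result or the most favourable of several. No form is the obvious carrier of the aim, because the one CNS symptom scale that the protocol names is not scheduled.

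The second issue stands apart from the first. Patients enter because they have symptoms, they know that they have been switched, and there is no comparison group. Regression to the mean and expectation can each produce improvement without any drug effect. Naming one endpoint in advance would limit selection but would not remove this problem. Taken at face value, the aim and Potential Scientific Problems together would allow one selected form and visit to be reported as a significant drug effect.

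**Working it through.** The documents give no sample size, power, alpha or SD, so there is no figure to reproduce. The calculation below is an illustration and applies only if results are presented as tests.

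**1. Counting the comparisons** (Study Calendar; assumes one score per form)
- Two focus forms (sleep; fine motor/ADL) × 2 visits = 4
- Adding Upper Extremity 7a: 3 × 2 = 6
- All scheduled forms: 4 × 2 = 8

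If a form's guidelines yield more than one score, the count is higher.

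**2. Chance of at least one false improvement**

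Assumptions not in the documents: two-sided 5% per comparison, so 2.5% in the direction of improvement; no true change; no adjustment; a common correlation ρ between comparisons.

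- Independent (ρ = 0): P = 1 − 0.975^k. For k = 4 this is 1 − 0.9037 = 0.0963; for k = 8 it is 1 − 0.8167 = 0.1833.
- Correlated: P = 1 − ∫ φ(z) Φ((1.96 − √ρ z)/√(1 − ρ))^k dz.

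| k | ρ = 0 | 0.3 | 0.5 | 0.7 | 0.9 |
|---|---|---|---|---|---|
| 1 | 2.5% | 2.5% | 2.5% | 2.5% | 2.5% |
| 4 | 9.6% | 8.7% | 7.8% | 6.5% | 4.7% |
| 6 | 14.1% | 12.2% | 10.4% | 8.2% | 5.4% |
| 8 | 18.3% | 15.2% | 12.5% | 9.5% | 6.0% |

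Repeated scores from the same patients are likely to be positively correlated, so the independent column is best read as an upper end.

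**3. Attribution**

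The documents contain no estimate of how much these scores would change without a switch, so the size of any non-drug change cannot be derived. The argument is qualitative: selection on symptoms, knowledge of the switch and no control group leave non-drug explanations open.

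**4. Precision if estimates are reported instead**

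Half-width of a 95% CI for a mean paired change, in units of the SD of change: t(0.975, n − 1)/√n. The values of n are assumed.
- n = 10: 2.262/3.162 = 0.72
- n = 20: 2.093/4.472 = 0.47
- n = 40: 2.023/6.325 = 0.32

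**The case against.** The strongest reply is that this is a pilot whose methods section disclaims testing, whose named tests are confined to descriptive analyses, and which sets no alpha or success rule. Only one word in the aim suggests a test, and it may mean clinically meaningful. Much of this stands. If Outcome Measure(s) governs, several unranked outcomes are acceptable and no multiplicity control is needed. But the protocol does not say that it governs, and if the word is meant clinically, no threshold is given.

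It is also fair to say that the before-after comparison is present at design level, since each patient is described as their own control. What is missing is the estimator or test of change. Nor is symptom improvement the only objective: Background and Significance also proposes to evaluate the reliability and validity of CNS-specific instruments.

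Preliminary Studies/Progress Report says the design will resemble that of a cited study. That does not fill the gap, because no endpoint is carried over into this protocol.

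Two stronger readings are tempting. One is that the plan already commits a multiplicity error or intends to pick the best result. The documents do not show this: they specify no confirmatory test, so the risk is conditional. The other is that any improvement seen will be a non-drug effect of some calculable size. The documents give no basis for such a figure.

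**Conclusion.** The point holds in two parts. First, the aim and the stated purpose conflict, and the form, visit and paired analysis are left open. If the aim's wording is used to claim significance, the chance of a false improvement rises from 2.5% to between 4.7% and 9.6% (4 comparisons) or between 6.0% and 18.3% (8 comparisons). These ranges rest on the assumed 5% level, one score per form and correlations from 0.9 down to 0; none of them describes this trial's actual error rate. Second, the statements that no scientific problem is expected and that improvement may not be placebo related are unsupported by the design, whichever purpose governs. This should be corrected. It does not make the pilot invalid, and the data collection can stand as planned.

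**What to change.** 1. **Aim.** Reword it as estimating the within-patient change from baseline at M1 and M6 in each scheduled patient-reported score relevant to CNS symptoms and quality of life. Remove the word significant.
2. **Data Analysis Plan.** State that the mean paired change, its t-based 95% CI and the number of patients contributing will be reported for every scheduled score at both visits. Make no significance claim, and do not treat an interval that excludes zero as one.
3. **Potential Scientific Problems.** Replace both statements (no problem expected; improvement may not be placebo related) with one saying that, without a control group, change cannot be attributed to the switch.
4. **Background and Significance.** State that the scheduled forms are the study's measures, and remove the CNS Symptom Rating Scale and Quality of Life Index, which are not scheduled.

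If the sponsor keeps a test, it should name one score, one visit and a paired test before analysis, label everything else exploratory, and keep the attribution statement.

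**Cost.** Text edits in four places, with no new visits, data or patients. The study can make no confirmatory claim, which Outcome Measure(s) already accepts, and CNS symptoms are covered only through the scheduled forms.

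### The general CNS-symptom hypothesis and the two named CNS instruments are not carried into the scheduled forms, whose titles give no pre-switch score for headache or concentration

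*Combined protocol and SAP*

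**What the plan says.** **What the opening sections promise.** Hypotheses and Specific Aims predicts that once-daily Envarsus XR "will have significant improvement in the patients reported CNS symptoms", with no limit to particular symptoms. Background and Significance then states: "We will evaluate the reliability and validity CNS-specific outcome instruments (CNS Symptom Rating Scale; higher scores = increased severity". The same sentence adds a second instrument, "Quality of Life Index (higher scores = better CNS-specific HRQL) in renal transplant patients". Later in that section the design is described as one in which the "patient will report objectively their experience related to CNS symptoms using a standard questionnaire before starting on Envarsus XR".

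**Which symptoms are meant.** Background and Significance says "The majority of the neurotoxicity events in tacrolimus treated transplant patients are headache and tremor". Further on it gives four examples of the CNS effects that the switch should help patients avoid: tremor, headache, difficulty concentrating and disturbed sleep. Entry is open to patients "18+ years of age with some CNS problems secondary to Prograf (tacrolimus", so any CNS complaint attributed to the drug qualifies.

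**What is collected.** Outcome Measure(s) expects quality-of-life gains "related to sleep disturbance and upper extremity fine motor skills/ADL". The section on procedures and data collection tools has a PROMIS questionnaire completed before the switch and repeated at 1 and 6 months with the same focus. It lists four forms: one on sleep disturbance, two on the upper extremity and one on global health. The Study Calendar marks these four at baseline, M1 and M6.

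**How they are analysed.** The Data Analysis Plan defines internal consistency reliability in general terms. It names no instrument and gives no method for validity.

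**The concern.** The hypothesis and Background describe a study of CNS symptoms in general, with a dedicated symptom scale. The outcome, procedure and calendar sections describe a study of sleep, hand and arm function and global health. A reader of the final report would not know which of the two had been done.

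The mismatch matters because of the design. There is no comparison group, and Preliminary Studies/Progress Report says "each patient will serve as its own control". All the information about a symptom then lies in the difference between a score before the switch and the same score after it. A symptom with no pre-switch score has no estimable change. Headache is one of the two events that the protocol puts in the majority, yet no form is identified as scoring it. The planned evaluation of the CNS Symptom Rating Scale likewise has no scheduled data behind it.

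**Working it through.** The documents state no sample size, power, effect size or standard deviation, so there is no figure to reproduce. The check sets the sections side by side.

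**Step 1: the named instruments.** Inputs are the two instruments in Background and Significance and the four forms in the data collection section and Study Calendar.

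| Instrument named in the Background | In the questionnaire list | In the Study Calendar | In the Data Analysis Plan |
|---|---|---|---|
| CNS Symptom Rating Scale | No | No | No |
| Quality of Life Index (CNS-specific) | No | No | No |

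By name, 0 of 2 instruments are scheduled. The Index might be loose wording for the quality-of-life forms that are scheduled, but none of those is described as CNS-specific. Nothing on the list could be the symptom rating scale under another name without further explanation.

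**Step 2: the symptoms.** Inputs are the four CNS effects in the Background and the titles of the four forms.

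| CNS effect | Form whose title covers it | Titled score before the switch |
|---|---|---|
| Sleep disturbance | Sleep form | Yes, directly |
| Tremor | Two upper-extremity forms | Indirectly, through function |
| Headache | None | None |
| Difficulty concentrating | None | None |

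By title, 1 of 4 effects is scored directly, 1 of 4 indirectly, and 2 of 4 not at all. The global health form names no symptom in its title.

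**Step 3: other pre-switch information.** Entry requires a CNS problem, and the chart review covers medical history. Either may show that a patient had headaches before the switch. Neither yields a score, and neither is a planned outcome, so they do not supply the before-and-after pair that the design needs.

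**Step 4: reliability and validity.** The reliability paragraph could be applied to the forms that are collected. It cannot be applied to the CNS Symptom Rating Scale, which generates no data. For validity there is no method for any instrument.

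**Step 5: consistency among the later sections.** Outcome Measure(s) and the repeat-questionnaire text point to sleep and upper-extremity function. The form list and calendar contain the same four forms. These sections agree with one another; the disagreement is between them and the opening sections.

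**The case against.** The strongest reply is that this is a pilot, and Outcome Measure(s) says outright that the approach is meant to generate hypotheses and not to test them. The later sections also agree on a narrower target, sleep is itself one of the listed CNS effects, tremor is reached through function, and a PROMIS questionnaire before the switch partly meets the Background's promise. On this view, all that is left is one stray Background sentence and a hypothesis worded too broadly.

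Much of that stands. It lowers the weight of the point and shows that a change of wording can resolve it. It does not remove the point. Generating a hypothesis about headache still requires observing headache before and after the switch, and the stated hypothesis still predicts significant improvement in CNS symptoms without limit.

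Four stronger readings are tempting, and the documents do not support them.

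- A reader might infer that CNS symptoms are not measured at all. Sleep is, directly, and tremor is, indirectly.
- A reader might infer that the forms cannot capture headache or concentration. Their items are not in the documents, so whether the global health form touches either symptom cannot be settled here.
- A reader might count the empty baseline cell for adverse events as a further defect. Baseline is when the switch takes place, and adverse events are recorded after it, so the blank is not an error.
- A reader might infer that broad entry dilutes the mean change by some stated factor. The documents give neither the mix of complaints at entry nor any standard deviation, so any such factor would rest on assumption alone.

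**Conclusion.** The point holds as an inconsistency of scope between the opening sections and the operative ones. As written, the plan supports a description of change in sleep disturbance, upper-extremity function and global health. It does not support a conclusion on CNS symptoms in general, and it provides no data for evaluating the named symptom scale.

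The general conclusion rests on two assumptions: that the form titles reflect their content, and that the calendar's global health entry is the global health scale on the list. If the items proved to include headache and concentration, the gap in symptom coverage would shrink, although those items would still have to be named as outcomes. The missing instruments would remain unexplained either way. The effect on this trial's numerical result cannot be computed. The point should be fixed, and preferably before the first patient is switched.

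**What to change.** Choose one of two courses before enrolment.

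1. **Measure what the hypothesis states.** Add one self-administered, patient-reported CNS symptom measure covering headache, tremor and concentration at Baseline (before the switch), M1 and M6, and tie the hypothesis to its change. The CNS Symptom Rating Scale could serve if the sponsor confirms its content and scoring. State how validity will be assessed or drop that aim, and say whether the Quality of Life Index is one of the listed forms or delete it. The cost is one more form at three existing visits; its length, and so the burden on patients, cannot be judged from the documents.

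2. **State what is measured.** Restrict the hypothesis and conclusions to sleep disturbance and upper-extremity function, as Outcome Measure(s) already does. Delete the Background sentence on the two scales, and apply the reliability paragraph of the Data Analysis Plan to the forms collected. The cost is a change of wording and giving up any conclusion on headache or concentration.

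The documents do not show whether enrolment has begun. If it has, take the second course, because a baseline score that was not collected before the switch cannot be recovered afterwards.
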